## 1.0 BACKGROUND AND RATIONALE

### 1.1 Study Synopsis

LCCC 1841 is a multicenter open-label, single-arm, pilot study designed to investigate the antitumor effects of acalabrutinib in subjects with relapsed primary central nervous system lymphoma (PCNSL), and relapsed secondary CNS lymphoma (SCNSL) with no evidence of current systemic disease. Subjects with the following histological subtypes of lymphoma will be included in the study: diffuse large B-cell lymphoma (DLBCL, all subtypes); mantle cell lymphoma (MCL, all subtypes); plasmablastic lymphoma, and lymphoplasmacytic lymphoma. Up to 16 subjects will receive acalabrutinib at the dose of 100 mg approximately every 12 hours (See Study Schema) to attain a total of 15 evaluable subjects as defined in Section 8.4. If the study shows a positive effect of acalabrutinib in treating CNS lymphomas, acalabrutinib could become the standard relapsed CNS lymphoma regimen, not only for PCNSL, but also in certain subtypes of SCNSL. Any complete responses to acalabrutinib treatment will be clinically notable as spontaneous remissions do not occur.

In a previous study, ibrutinib showed a CR rate of 45% and an ORR of 68% [1]; in another study [2], ibrutinib showed a CR rate of 17% and an ORR of 55%. Thus, in order to recommend further investigation of acalabrutinib as a regimen for primary CNS lymphoma, acalabrutinib treatment must show an overall response rate (ORR) of at least 70%, which would demonstrate that it is not inferior to previously approved regimens.

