### 4.1 Inclusion Criteria

- 4.1.1 Willing and able to participate in all required evaluations and procedures in this study protocol, including swallowing capsules and tablets without difficulty.
- 4.1.2 Ability to understand the purpose and risks of the study and provide signed and dated informed consent and authorization to use protected health information (in accordance with national and local patient privacy regulations)..
- 4.1.3 Age  $\geq 18$  years at the time of consent.
- 4.1.4 Subject has adequate performance status as defined by [ECOG](#) of  $\leq 2$ .  
*(Note: Performance status can be assessed after administration of corticosteroids.)*
- 4.1.5 Subject has histological confirmation of biopsy-proven CNS lymphoma OR MRI findings consistent with CNS lymphoma if biopsy is not possible (due to inaccessible location). Subjects with intra-ocular lymphoma will not be excluded as long as there is also parenchymal disease.
- 4.1.6 Subject has B-cell Non-Hodgkin Lymphoma.
- 4.1.7 Subject has no evidence of systemic involvement of lymphoma confirmed by CT or PET-CT imaging within 28 days prior to first dosing in the study.
- 4.1.8 Subject must have received at least one prior line of chemotherapy for primary or secondary CNS lymphoma. There is no limit on the number of prior treatment regimens.
- 4.1.9 Subject has adequate organ function as demonstrated by:

System	Laboratory Value
Hematological*	
Absolute Neutrophil Count (ANC)	$\geq 1 \times 10^9/\text{L}$
Platelets	$\geq 75 \times 10^9/\text{L}$
Renal*	
Calculated creatinine clearance	$\geq 30 \text{ mL/min}$ using the Cockcroft-Gault formula ( Appendix B )

Hepatic*	
Bilirubin	$\leq 1.5 \times$ upper limit of normal (ULN). Subjects with Gilbert's syndrome may be enrolled despite a total bilirubin level $>1.5$ mg/dL if their conjugated bilirubin is $<1.5 \times$ ULN)
Aspartate aminotransferase (AST)	$\leq 2.5 \times$ ULN
Alanine aminotransferase (ALT)	$\leq 2.5 \times$ ULN
Coagulation*	
International Normalized Ratio (INR) or Prothrombin Time (PT) and Activated Partial Thromboplastin Time (aPTT)	$\leq 2 \times$ ULN (in the absence of lupus anticoagulant)

**4.1.10** Subjects with a prior or concurrent malignancy whose natural history or treatment does not have the potential to interfere with the safety or efficacy assessment of the treatment are eligible for this trial.

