#### **7.4.4 Rubidium-82 Positron-Emission Tomography**

Rb PET/CT will be performed at screening, at Cycle 3 Day 1 and at Cycle 7 Day 1 in the first 5 subjects at the University of North Carolina with parenchymal brain disease who consent to this testing. We will quantify the uptake by calculating SUV variables (SUVmax and SUVave of normal brain, subcutaneous fat, lung and mediastinal blood pool) and visually assessing (using the Brain Lymphoma Rubidium Visual Scoring Scale: [Appendix H](#)) the uptake at various time points at the tumor site. We will also derive various SUV-based and visual quantitative (similar to Deauville Score) scores by comparing the SUV and visual score of the tumor to the SUV and visual scores of normal structures captured on the images, e.g. lung, subcutaneous fat and aorta.

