**Table 3. Anatomic and Radiographic Endpoint Definitions**

Endpoint Definitions			
Endpoint	Response Category	Definition	Point of Measurement
Overall survival	All patients	Death as a result of any cause	Entry onto trial
Event-free survival	All patients	Failure or death as a result of any cause	Entry onto trial
Progression-free survival	All patients	Disease progression or death as a result of PCNSL	Entry onto trial
Disease-free survival	CR, CRu	Time to relapse	First documentation of response
Response duration	CR, CRu, PR	Time to relapse or progression	First documentation of response

*CR requires the following:*

(1) Complete disappearance of all enhancing abnormalities on gadolinium-enhanced MRI.

(2) No evidence of active ocular lymphoma as defined by absence of cells in the vitreous and resolution of any previously documented retinal or optic nerve infiltrates. Chronic changes of the retinal pigment epithelium in the setting of a prior retinal or optic nerve infiltrate does not preclude the definition of a CR. All patients with initial involvement of the eyes on baseline evaluation should have a detailed follow-up evaluation including dilated fundus examination and color photographs of the posterior pole of the eye. Repeat ophthalmologic evaluation is not required for patients without evidence of ocular lymphoma at baseline or interval development of ocular symptoms.

(3) At the time a CR is determined, the patient should have discontinued use of all corticosteroids for at least 2 weeks. Rare exceptions may be made for those patients receiving corticosteroids for another diagnosis (e.g., panhypopituitarism).

*CR/unconfirmed (CRu) includes those patients who fulfill the criteria for CR with the following features/limitations:*

(1) Any patient who fulfills all criteria for CR but continues to require corticosteroid therapy at any dose should be considered an unconfirmed CR. This is critical because corticosteroids may be oncolytic in treating occult tumor. In addition, corticosteroids may decrease gadolinium enhancement on MRI.

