(2) Some patients will have a small but persistent enhancing abnormality on MRI related to biopsy or focal hemorrhage. It is often difficult to ascertain whether this represents a residual nidus of tumor or scar tissue. Adjunctive radiologic studies such as single-photon emission computed tomography or positron emission tomography may be helpful, but often the nature of these abnormalities may only be determined by observing the patient with serial scans. If the type of abnormality does not change or slowly involutes over time without therapy and corticosteroids, it is reasonable to categorize it as a CR.

(3) Patients with a persistent minor abnormality on follow-up ophthalmologic examination (persistent non-malignant cells in the vitreous, alteration of the retina/optic nerve that is not consistent with tumor infiltration) may be considered a CRu if this abnormality is unlikely to represent ocular lymphoma.

*Partial response (PR) requires all of the following:*

(1) A  $\geq 50\%$  decrease in the contrast-enhancing lesion seen on MRI as compared with baseline imaging.

(2) Corticosteroid dose is irrelevant to the determination of PR.

(3) Ophthalmologic examination should show a decrease in the vitreous cell count or retinal/optic nerve cellular infiltrate but may continue to show persistent malignant or suspicious cells. Color photos of the posterior pole of the eye should be obtained to document improvement in retinal/optic nerve infiltrates.

(4) No new sites of disease.

Stable disease is defined as less than a PR but is not progressive disease.

*Progressive disease requires the following:*

(1) A more than 25% increase in the contrast-enhancing lesion seen on MRI as compared with baseline or best response (comparison should be made to the smallest of multiple lesions).

(2) Progression of ocular disease as indicated by an increase in the vitreous cell count or progressive retinal or optic nerve infiltration.

(3) Appearance of any new lesion or site of disease (ocular, leptomeningeal or systemic) during or at the end of therapy.

*Relapsed disease (only applicable to patients with a prior CR, CRu) requires the following:*

(1) Appearance of any new lesion.

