### 10.2 Sample Size, Accrual and Duration of Accrual

We plan to accrue up to 16 subjects to ensure planned (evaluable, in terms of status of overall response) sample size of 15. With 15 evaluable subjects, we reject the null hypothesis when we observe  $> 9$  (10 or more) responders. This design gives power 72% with one-sided type 1 error 0.15. We will replace non-evaluable (e.g., loss to follow-up) cases by new subjects to guarantee planned sample size.

Accrual for this trial is expected to take approximately 24-36 months.

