### 10.3 Data Analysis Plans

Analysis of efficacy will be conducted following pre-specified inference rule on rejecting the null hypothesis:  $H_0: \text{ORR} \leq 50\%$ . Specifically, we will reject the null hypothesis if and only if there are  $>9$  ORs in the 15 subjects. The main analysis is inferential because we frame it as a hypothesis-testing problem. We will also calculate 2-sided 95% clopper-Pearson confidence interval for ORR.

Secondary endpoints include PFS, CR, DoR, overall survival, and safety/toxicity. Analyses of secondary endpoints will be descriptive. Specifically, time-to-event outcomes like PFS, DoR, and OS will be analyzed using Kaplan-Meier method, and Kaplan-Meier survival curves will be provided. Categorical outcomes like CR, and safety/toxicity (different types of AEs) will be summarized using frequencies.

- For the primary outcome, ORR, there should be no missing data. We will replace non-evaluable cases with new subjects so that the total sample size of 15 evaluable subjects is guaranteed.
- There is only one test for the primary endpoint and hence there is no multiplicity issue.

Per exploratory endpoints:

[REDACTED]

[REDACTED]

[REDACTED]

[REDACTED]

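### No contrast-enhancing lesion is required on the baseline MRI, so a subject whose MRI response cannot be determined can fill one of the 15 evaluable slots

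*Combined protocol and SAP*

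**What the plan says.** **Entry.** Criterion 4.1.5 asks that "Subject has histological confirmation of biopsy-proven CNS lymphoma OR MRI findings consistent with CNS lymphoma if biopsy is not possible". The histology carries no date, and a subject who has it needs no particular MRI finding. Parenchymal disease is demanded only of subjects who also have intra-ocular lymphoma. Criterion 4.2.5 excludes CSF disease only if it needs continuing intrathecal chemotherapy. Section 7.1.7 and footnote 9 of the Time and Events Table schedule a brain MRI in the 28 days before dosing, but state nothing that it must show.

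**Response.** The primary endpoint (3.1) is PR plus CR at 2 months. Under 8.4.1, every PR item must be met; the first is at least a 50% "decrease in the contrast-enhancing lesion seen on MRI as compared with baseline imaging". The first CR item is "Complete disappearance of all enhancing abnormalities on gadolinium-enhanced MRI". CR also has an ocular item and a period off corticosteroids; PR also has an ocular item and excludes new sites. CSF cytology is not an item for either, and the only CSF sampling in the schedule is for drug uptake.

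**Who counts.** Section 8.4.1 makes a subject evaluable for efficacy on drug exposure alone (one cycle). Section 10.2 instead describes evaluability by whether overall response status is available. It replaces non-evaluable cases, giving loss to follow-up as its example, and accrues at most 16 subjects to obtain 15. Section 10.3 expects no missing ORR data.

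**The concern.** The response criteria presuppose something on the baseline MRI that the entry criteria do not guarantee. A subject with earlier biopsy-proven disease, whose current disease is confined to the CSF and shows no enhancement, satisfies 4.1.5 and is not caught by 4.2.5. A 50% decrease from nothing cannot be calculated, so PR is undefined. The MRI item of CR is already true on Day 1 if it is read as absence of enhancement, and can never be met if disappearance is read strictly. The plan does not say which reading applies, so each site would choose.

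The subject nevertheless enters the denominator after one cycle. The trial has one inferential test, on 15 subjects with a fixed cut-off of 10 responders, so the scoring of one subject can change the conclusion.

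**Working it through.** **Inputs.** From 10.1 to 10.3: null ORR 50%, target ORR 70%, n = 15, reject the null with 10 or more responders. From 10.2: "This design gives power 72% with one-sided type 1 error 0.15". Let k be the number of the 15 subjects with no baseline enhancement. The documents give no value, so k is an assumption.

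**1. The plan's own figures.** By exact binomial:
- Type I error = P(Bin(15, 0.5) ≥ 10) = (3003 + 1365 + 455 + 105 + 15 + 1)/32768 = 4944/32768 = 0.151.
- Power = P(Bin(15, 0.7) ≥ 10) = 0.722.

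Both agree with the stated values at the precision printed.

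**2. Outer bounds.** If all k subjects are always scored CR, the other 15 − k must supply 10 − k responders: P(Bin(15 − k, p) ≥ 10 − k). If all are always scored non-responders, the other 15 − k must supply all 10: P(Bin(15 − k, p) ≥ 10).

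| k (assumed) | Scoring | Type I error (p = 0.5) | Power (p = 0.7) |
|---|---|---|---|
| 0 | as planned | 0.151 | 0.722 |
| 1 | always CR | 0.212 | 0.781 |
| 1 | never a response | 0.090 | 0.584 |
| 2 | always CR | 0.291 | 0.835 |
| 2 | never a response | 0.046 | 0.421 |

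For k = 1 the type I errors are 3473/16384 = 0.212 and 1471/16384 = 0.090.

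**3. Between the bounds.** If one such subject is scored CR with probability s (an assumption):
- Type I error = s × 0.212 + (1 − s) × 0.090. At s = 0.5 this is 0.151, no change from plan. At s = 0.7 it is 0.175.
- Power = s × 0.781 + (1 − s) × 0.584. At s = 0.7 this is 0.722, again no change.

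**4. How likely one is.** If a share q of enrolled subjects has no baseline enhancement (an assumption), the chance of at least one among 15 is 1 − (1 − q)^15. Average power when all are scored non-responders is P(Bin(15, 0.7(1 − q)) ≥ 10). Average type I error when all are scored CR is P(Bin(15, q + 0.5(1 − q)) ≥ 10).

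| q (assumed) | At least one in 15 | Power, never a response | Type I error, always CR |
|---|---|---|---|
| 2% | 26% | 0.679 | 0.170 |
| 5% | 54% | 0.613 | 0.201 |
| 10% | 79% | 0.499 | 0.261 |

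**The case against.** The strongest reply is that the gap is narrow and partly covered. The trial is for relapsed or refractory disease, most of which will probably show on MRI. The route for subjects who cannot be biopsied itself requires MRI findings. Section 10.2 ties evaluability to response status and provides for replacement, so a subject whose response cannot be determined could arguably be replaced. This is also a pilot with a one-sided error of 0.15, intended to give preliminary data; at q = 2% the average power loss is about 4 points (0.722 to 0.679).

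Most of that stands as a limit on frequency and size. It does not close the gap. The histology route needs no MRI finding, and the replacement wording in 10.2 conflicts with the exposure-only rule in 8.4.1. A cap of 16 for 15 slots leaves one replacement.

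Four stronger readings are tempting, and the documents do not support them:
- **That response rests on enhancing lesions alone.** It does not: ocular items apply to both categories, a corticosteroid item to CR, and a new-site item to PR. These are added conditions, however. Without eye disease, the enhancing lesion is the only measure of shrinkage.
- **That such a subject is a certain responder.** A new lesion or site makes the subject progressive. Continuing corticosteroids makes an otherwise complete response CRu, and 3.1 counts PR and CR without mentioning CRu. The figure of 0.212 is therefore a ceiling.
- **That small lesions pose the same problem.** A small enhancing lesion can disappear, persist or grow, so its outcome is open. The documents give no size threshold.
- **That the rubidium PET wording, "with parenchymal brain disease who consent to this testing", proves other subjects may lack brain lesions.** Section 1.6 and footnote 10 of the Time and Events Table describe the same subset without that phrase, so little can be inferred from it.

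**Conclusion.** The concern holds in limited form. Followed as written, the plan can admit a subject with no enhancing baseline lesion and count that subject among the 15, with PR undefined and CR dependent on interpretation.

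For one such subject, type I error lies between 0.090 and 0.212 (planned 0.151) and power between 0.584 and 0.781 (planned 0.722), depending on scoring; at intermediate scoring there may be no distortion. These are sensitivity bounds, not estimates. They assume that the other 14 subjects respond independently at the design rates and that the 10-responder cut-off is kept. How many such subjects will be enrolled is unknown. The point merits correction because the test is small and the remedy uses an MRI that is already mandated.

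**What to change.** 1. Add to 4.1.5 that at least one contrast-enhancing CNS lesion must be present on the baseline gadolinium-enhanced MRI. Whether to set a minimum size, and what it should be, is for the sponsor.
2. Align 8.4.1 with 10.2: a subject without such a lesion is not evaluable for ORR and is replaced within the cap of 16. The cap allows one replacement in total (16 − 15 = 1), so the eligibility line has to do most of the work.
3. For subjects already enrolled, identify those without baseline enhancement from the baseline MRI alone, before the analysis, and report ORR with and without them. Do not simply score them as non-responders: that is the case in which one subject cuts power to 0.584. Removing one without replacement while keeping the cut-off of 10 has the same effect, since P(Bin(14, 0.7) ≥ 10) = 0.584. If 15 evaluable subjects cannot be restored, present the ORR without them as an estimate with its confidence interval.

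**Cost.** A protocol amendment with IRB approval, and slightly slower accrual in a rare disease where Amendment 1 already dropped a 28-patient accrual goal as not feasible in a timely fashion. No new procedure is needed.

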## 4.2 Exclusion Criteria

Subjects meeting any of the following exclusion criteria will *not* be able to participate in this study

- 4.2.1** Prior cancer treatment that was completed less than 14 days prior to Day 1 of study dosing or if subject has not recovered from all reversible acute toxic effects of the regimen to grade  $\leq 1$  or baseline.
- 4.2.2** Prior brain radiotherapy under the following conditions:
- Whole-brain radiotherapy (WBRT) that was completed less than 28 days prior to Day 1 of study dosing
  - Stereotactic radiosurgery (SRS) that was completed less than 14 days prior to Day 1 of study dosing.
- 4.2.3** Currently receiving or has received an investigational agent within 28 days of first dosing with study treatment. Subjects should not currently be receiving investigational treatment or have received an investigational agent within 28 days of dosing.
- 4.2.4** Subject is pregnant or breastfeeding (*Note*: breast milk cannot be stored for future use while the mother is being treated on study).
- 4.2.5** Subject has active CSF involvement that requires ongoing intrathecal chemotherapy.
- 4.2.6** Previous exposure to a BTK inhibitor.
- 4.2.7** Subjects with severe hepatic insufficiency, as defined by [Child-Pugh Score](#)  $> 6$  ([Appendix C](#)).
- 4.2.8** Subject is receiving prohibited medications or treatments as listed in [Section 5.3](#) of the protocol that cannot be discontinued/replaced by an alternative therapy. Subject requires treatment with a strong cytochrome P450 3A4 (CYP3A4) inhibitor/inducer (please consult [Section 5.3](#)). Subjects may be eligible if they are medically able to discontinue CYP3A4 inhibitors/inducers at least 14 days before the first dose of study treatment.
- 4.2.9** Subject requires or receiving anticoagulation with warfarin or equivalent vitamin K antagonists (e.g., phenprocoumon) within 14 days of first dose of study drug. Subjects requires or is taking direct oral anticoagulants (e.g. apixaban, rivaroxaban, edoxaban, lovenox) within 7 days of first dose of study drug.
- 4.2.10** Subjects receiving capsule form of acalabrutinib may not be taking proton pump inhibitors (e.g., omeprazole, esomeprazole, lansoprazole, dextansoprazole, rabeprazole, or pantoprazole). Subjects receiving proton pump inhibitors who

switch to H2-receptor antagonists or antacids and subjects receiving tablet form of acalabrutinib are eligible for enrollment to this study.

[figure not shown]
- 4.2.11** Subject is currently receiving any chemotherapy, anticancer immunotherapy. *Note:* Subjects receiving corticosteroids will be eligible, but corticosteroids are expected to be tapered off as soon as possible from a clinical standpoint.
- 4.2.12** Subject has clinically significant cardiovascular disease such as ventricular dysfunction, symptomatic coronary artery disease, uncontrolled or symptomatic arrhythmias, congestive heart failure, or myocardial infarction within 6 months of screening, or any Class 3 or 4 cardiac disease as defined by the New York Heart Association (NYHA) Functional Classification ([Appendix D](#)) at screening. Subjects with controlled, asymptomatic atrial fibrillation during screening can enroll on study.
- 4.2.13** Subject has familial short QT syndrome.
- 4.2.14** Subject has a history of malabsorption syndrome, disease significantly affecting gastrointestinal function, or resection of the stomach or small bowel, symptomatic inflammatory bowel disease, partial or complete bowel obstruction, or gastric restrictions and bariatric surgery, such as gastric bypass that is likely to affect absorption.
- 4.2.15** Subject has a known history of infection with HIV or any uncontrolled active significant infection (e.g., bacterial, viral or fungal).
- 4.2.16** Subject has a known history of drug-specific hypersensitivity or anaphylaxis to acalabrutinib (including active ingredient or excipient components).
- 4.2.17** Subject has active bleeding or history of bleeding diathesis (e.g., hemophilia or von Willebrand disease).
- 4.2.18** Subject has a history of uncontrolled AIHA (autoimmune hemolytic anemia) or ITP (idiopathic thrombocytopenic purpura).
- 4.2.19** Subject has a history of significant cerebrovascular disease/event, including stroke or intracranial hemorrhage, within 6 months before the first dose of acalabrutinib.
- 4.2.20** Subject had major surgical procedure within 28 days of first dose of acalabrutinib. *Note:* If a subject had major surgery, they must have recovered adequately from any toxicity and/or complications from the intervention before the first dose of acalabrutinib.
- 4.2.21** Subjects who are hepatitis B core antibody (anti-HBc) positive and who are hepatitis B surface antigen (HBsAg) negative will need to have a negative PCR result before randomization and must be willing to undergo DNA PCR testing during the study. Subjects who are core antibody positive and viral load negative

- must receive entecavir prophylaxis. Those who are HbsAg-positive or hepatitis B PCR positive will be excluded.
- 4.2.22** Subjects who are hepatitis C antibody positive must have a negative polymerase chain reaction (PCR) result. Those who are hepatitis C PCR positive will be excluded.
- 4.2.23** Evidence of disease (such as severe or uncontrolled systemic diseases, including uncontrolled hypertension and renal transplant) that, in the investigator's opinion, make it undesirable for the patient to participate in the study or that would jeopardize compliance with the protocol.
- 4.2.24** History of or ongoing confirmed progressive multifocal leukoencephalopathy (PML).
- 4.2.25** Received a live virus vaccination within 28 days of first dose of study drug.
- 4.2.26** Any active significant infection (e.g., bacterial, viral or fungal, including subjects with positive cytomegalovirus [CMV] DNA polymerase chain reaction [PCR]).
- 4.2.27** Concurrent participation in another therapeutic clinical trial.
- 4.2.28** Current life-threatening illness, medical condition, or organ system dysfunction which, in the Investigator's opinion, could compromise the subject's safety or put the study at risk.

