### 5.3 Prohibited and Concomitant Medications

CYP3A-mediated oxidation is the major route of metabolism of acalabrutinib in humans. CYP3A4/5 is the predominant CYP isoform responsible for metabolism of acalabrutinib. Therefore, additional strong or moderate inhibitors of CYP3A4 and strong and moderate inducers of CYP3A4 are prohibited.

A frequently updated P450 drug interaction table is available at: <http://medicine.iupui.edu/clinpharm/ddis/>.

If medically justified, subjects may be enrolled if such inhibitors or inducers can be discontinued or alternative drugs that do not affect these enzymes can be substituted at least 7 days before first dose of acalabrutinib.

Acalabrutinib is not a potent direct inhibitor of CYP3A4 and is not anticipated to be a perpetrator of drug interactions at the level of systemic inhibition of CYP3A4.

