### **11.5.2 Single Subject Exceptions**

Eligibility single subject exceptions are not permitted for Lineberger Comprehensive Cancer Center Investigator Initiated Trials under any circumstances. Other types of single subject exceptions may be allowed if proper

regulatory review has been completed in accordance with Lineberger Comprehensive Cancer Center's Single Subject Exceptions Policy.

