## 13.0 APPENDICES

### 13.1 Appendix A: Prohibited Medications or Those to Use with Caution

Acalabrutinib is predominantly metabolized by CYP3A enzymes, and to a minor extent, by glutathione conjugation and amide hydrolysis. The most abundant circulating active metabolite in human is ACP-5862, which is formed by CYP3A-mediated oxidation. Strong inhibitors have the potential to increase plasma concentrations of acalabrutinib and decrease plasma concentrations of its active metabolites. Strong inhibitors of CYP3A enzymes are prohibited in this trial. Other drugs known to induce or inhibit CYP3A enzymes should be used with caution, or alternative treatments considered. *Note: this is not an exhaustive list and further details can be found at <https://drug-interactions.medicine.iu.edu/MainTable.aspx> and at Expert Opin. Drug Metab Toxicol (2013) 9(6) 737-751. If a drug appears on more than one list follow the more conservative rule.*

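### Exclusion 4.2.8 and Section 5.3 set different CYP3A4 washouts (14 and 7 days), and Section 5.3 and Appendix A prohibit different classes of CYP3A drug

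*Combined protocol and SAP*

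**What the plan says.** Exclusion 4.2.8 has three parts. It excludes subjects on any drug prohibited by Section 5.3 that cannot be stopped or replaced. It excludes anyone for whom this holds: "Subject requires treatment with a strong cytochrome P450 3A4 (CYP3A4) inhibitor/inducer", again pointing to 5.3. It then relaxes this for subjects who are "medically able to discontinue CYP3A4 inhibitors/inducers at least 14 days before the first dose of study treatment", without saying which strengths it means.

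Section 5.3 states that "additional strong or moderate inhibitors of CYP3A4 and strong and moderate inducers of CYP3A4 are prohibited". It goes on to allow enrolment, where medically justified, if such agents "can be discontinued or alternative drugs that do not affect these enzymes can be substituted at least 7 days before first dose of acalabrutinib". It also names CYP3A oxidation as the main way acalabrutinib is metabolised.

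Appendix A has a different scope: "Strong inhibitors of CYP3A enzymes are prohibited in this trial. Other drugs known to induce or inhibit CYP3A enzymes should be used with caution". It labels some inhibitors as strong, moderate or weak and lists inducers without labels. For a drug on more than one list, it asks the reader to take the stricter rule.

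Appendix E, the patient handout, repeats the lists under a title about prohibited drugs. Its text asks for careful use and gives neither a washout nor a ban by strength.

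Section 11.5.2 adds: "Eligibility single subject exceptions are not permitted".

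**The concern.** These are operative rules in the current text, not remnants in the amendment log. A site screening a subject who recently stopped an interacting drug gets one answer from the exclusion list and another from the section that the list cites. A site deciding whether a treated subject may take a moderate inhibitor gets one answer from 5.3 and another from Appendix A.

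Two things are at stake. One is whether an enrolment is compliant: with no exceptions allowed, a subject in the gap is either eligible or a breach. The other is uneven control of drug exposure across sites in a study of at most 16 subjects.

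**Working it through.** **Washout.** Inputs: 14 days (4.2.8) and 7 days (5.3). The difference is 14 − 7 = 7 days. Let d be the number of days between the last dose of the interacting drug and the first dose of acalabrutinib.

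- d of 14 or more: meets both.
- d from 7 to 13: meets 5.3, fails 4.2.8.
- d below 7: fails both.

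The 7 days in 5.3 could be read as attached only to substitution. That does not remove the conflict: a drug replaced 7 days before dosing was itself stopped 7 days before dosing, and discontinuation without replacement would then have no stated minimum.

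**Prohibited class.** The texts side by side:

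| Class | 4.2.8 (entry) | 5.3 | Appendix A |
|---|---|---|---|
| Strong inhibitor | named | prohibited | prohibited |
| Moderate inhibitor | through reference to 5.3 | prohibited | caution |
| Strong inducer | named | prohibited | caution |
| Moderate inducer | through reference to 5.3 | prohibited | caution |

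Section 5.3 and Appendix A agree on one row of four. Appendix A labels six drugs as moderate inhibitors: aprepitant, erythromycin, fluconazole, grapefruit juice, verapamil and diltiazem. Each is banned by 5.3 and allowed with caution by Appendix A.

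**Can the rule be applied from the lists?** Of 32 inhibitors in Appendix A, 9 are labelled strong, 6 moderate and 1 weak, so 32 − 16 = 16 have no label; voriconazole and ciprofloxacin are among them. None of the 15 inducers has a label. One listed inducer is glucocorticoids, while 4.2.11 admits subjects on corticosteroids and expects a taper. The protocol's own lists do not show whether the 5.3 ban reaches them.

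**Does Appendix A's tie-break settle it?** It concerns a drug that appears on more than one list. It does not mention washout length or a disagreement between sections.

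**Primary test.** Section 10.2 rejects the null with 10 or more responders of 15. The exact binomial tail P(X ≥ 10 | n = 15, p) is 0.1509 at p = 0.50 and 0.7216 at p = 0.70, in line with the stated 0.15 and 72%. Neither the washout nor the drug class enters this calculation.

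**The case against.** The strongest reply is that eligibility is not really open. Section 4 requires every criterion to be met and bars anyone who meets an exclusion. The allowance in 5.3 is permissive and sits outside Section 4. A 14-day stop satisfies both texts, and the coordinating centre verifies eligibility from source documents before treatment (Section 11.3). The first sentence of 4.2.8 also imports everything that 5.3 prohibits, so 4.2.8 is not a third, narrower class. All this is fair and limits how far sites would diverge at entry. But if Section 4 governs, the 7-day allowance in 5.3 is wrong as written, and precedence at entry does not settle what may be taken during treatment.

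A second reply is that 5.3 points to an external interaction table, so missing labels do not make its rule unusable. That also stands in part. The table cannot be checked here, and Appendix A would still state a different rule.

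A reader might infer more than the documents support:

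- **That a permitted moderate inhibitor at least doubles acalabrutinib exposure.** The fold-changes in the Appendix A footnotes define inhibitor classes in general and are not acalabrutinib results. Appendix A also says strong inhibitors raise the parent drug and lower its active metabolites. Section 1.5.1.1 puts ACP-5862 at 2 to 3 times the parent's AUC with about half its potency. The net effect on active drug is therefore not known from the text.
- **That the washout gap distorts plasma pharmacokinetics.** Plasma is sampled only on Cycle 1 Day 8 (Section 8.1, footnote 16). A subject who stopped 7 days before dosing is then 7 + 7 = 14 days off the drug, or 11 at the early end of the ±3-day window. Only the Day 1 CSF sample falls sooner, and subjects may miss it.
- **That toxicity or response is shown to be affected.** The link is directional only.
- **That the pharmacokinetic analysis ignores interacting drugs.** The exploratory analysis text in Section 10.3 is redacted, so this cannot be judged.

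**Conclusion.** The contradiction holds. Its size is a 7-day difference in washout, which leaves subjects who stopped 7 to 13 days before dosing with two answers, and a disagreement over three of four drug classes, including six named moderate inhibitors and all inducers that 5.3 bans. The documents do not show how many subjects would fall in the gap.

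Because CYP3A is the main metabolic route, inconsistent handling can alter exposure, but no magnitude for acalabrutinib can be stated. The stated type 1 error and power of the response-rate test do not change. The conclusion rests on reading the current text of 4.2.8, 5.3 and Appendix A literally. No view is taken on which washout or which scope of ban is right.

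**What to change.** The sponsor should:

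1. Reconcile 4.2.8, 5.3 and Appendix A to one washout and one prohibited class of its choosing, and word the Appendix E handout to match.
2. Add strength labels to the 16 unlabelled inhibitors and the 15 inducers, wherever the lists appear.
3. State how glucocorticoids, as a listed inducer, fit with 4.2.11.

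The cost is a wording amendment in four places plus labels on existing lists, with ethics approval because eligibility text changes. No new data and no change to sample size are needed.

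A pharmacokinetic flag for any listed inhibitor or inducer is not recommended. It would catch every corticosteroid-treated subject, so a comparison with and without flagged subjects in at most 16 could be uninformative.
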